## List of Abbreviations and Acronyms

AE – adverse event

AIDS – Acquired Immunodeficiency Syndrome

ALT – alanine aminotransferase

AST – aspartate aminotransferase

BUN – blood urea nitrogen

CBC – complete blood count

CDI – *Clostridium difficile* infection

CFR – Code of Federal Regulations

CLIA – Clinical Laboratory Improvement Amendments

DCF – data clarification form

eCRF – electronic case report form

FDA – Food and Drug Administration

FT – fecal transplant

GCPs – Good Clinical Practices

HIV – human immunodeficiency virus

IBD – inflammatory bowel disease

IBS – irritable bowel syndrome

ICF – informed consent form

ICH – International Council on Harmonisation

ICU – intensive care unit

IgG – Immunoglobulin

IRB – Institutional Review Board

IVIG – intravenous immunoglobulin

mL - milliliter

NA – not applicable

PAL – Product Accountability Log

PCR – polymerase chain reaction

REB – Research Ethics Board

SAE – serious adverse event

SAP – Statistical Analysis Plan

SAR – suspected adverse reaction

SOC – system organ class

SOP – standard operating procedure

USP – United States Pharmacopeia

VRE – vancomycin-resistant *enterococci*

**Synopsis**

Title	An Open-label Efficacy and Safety Assessment of Rebiotix RBX2660 (microbiota suspension) for the Treatment of Recurrent Clostridium difficile Infection
Investigational Product and Indication for Use	RBX2660 (microbiota suspension). RBX2660 is being studied for the treatment of adult subjects as an adjunct to antibiotics for the treatment of recurrent Clostridium difficile infection (CDI)
Control Product	Not applicable
Study Purpose	The purpose of this study is to evaluate the efficacy and safety of RBX2660 for the treatment of recurrent CDI in subjects who have had either a) at least two recurrences after a primary episode (primary episode + $\geq$ two recurrences, i.e., at least three episodes) and have completed at least two rounds of standard-of-care oral antibiotic therapy or b) have had at least two episodes of severe CDI resulting in hospitalization.
[REDACTED]	[REDACTED]
Objectives	
Primary Objective                      To compare the efficacy of one treatment with RBX2660 versus antibiotic-treated historical controls. (One treatment consists of 2 enemas of RBX2660 7 <math>\pm</math> 2 days apart.)
 
Secondary Objectives
 
 
1. To evaluate the safety of RBX2660.
 
2. To evaluate the effect of RBX2660 on pre-existing conditions other than recurrent CDI.
 
3. To evaluate quality of life as measured by the SF-36 Health Survey.
 
4. To evaluate the efficacy of C. difficile anti-infection therapies administered to confirmed treatment failures.
 


Study Design
	
This is a prospective, multicenter, open-label study assessing RBX2660 as an adjunct to antibiotics for the treatment of recurrent CDI. Up to approximately 150 subjects will be enrolled in this study. Efficacy of RBX2660, measured by the recurrence-free rate of CDI diarrhea without the need for retreatment with C. difficile anti-infective therapy or fecal transplant through 56 days after completion of study treatment with RBX2660, will be evaluated by comparing the recurrence-free rate observed in the study population to the recurrence-free rate identified from antibiotic-treated historical controls. Subjects who meet all inclusion and exclusion criteria, including having a positive C. difficile test within 60 days prior to enrollment and experiencing either a) at least two recurrences after a primary episode and have completed at least two rounds of standard-of-care oral antibiotic therapy or b) have had at least two episodes of severe CDI resulting in hospitalization prior to enrollment, will receive treatment with RBX2660. One completed study treatment consists of two RBX2660 enemas administered <math>7 \pm 2</math> days apart (no antibiotics between doses); the second enema may be administered sooner if CDI diarrhea reoccurs in less than 7 days. Subjects will already be taking or will start a course of antibiotics to control recurrent CDI diarrhea at the time of enrollment, [REDACTED]
 
[REDACTED]
 
[REDACTED]
 
[REDACTED]
 
[REDACTED]
 
[REDACTED] An in-office follow-up visit will occur at 8 weeks after completing study treatment for the assessment of AEs, efficacy, collection of the Subject Diary and blood tests. Telephone assessments for adverse events including serious adverse events (SAEs) and the new onset of chronic diseases and CDI symptoms will occur at weeks 1, 2, 3, and 4 and at 3, 6, and 12 months after completing study treatment. Assessment of SAEs and the new onset of chronic diseases will occur via phone call at 24 months after completing study treatment. Subjects will keep a detailed Subject Diary to allow for the assessment of solicited adverse events from the date of enrollment to 1 week after completing study treatment. Treatment failures (as determined by the site investigator at the time of CDI recurrence) are eligible to receive another therapy deemed most appropriate by their study investigator; see “Management of Treatment Failures,” below.


Study Dosing
	
A study treatment consists of two enemas (doses) of RBX2660 administered <math>7 \pm 2</math> days apart (the second enema may be administered sooner if CDI diarrhea reoccurs in less than 7 days).

Definition of Treatment Success	Treatment success is defined as: the absence of CDI diarrhea without the need for retreatment with C. difficile anti-infective therapy or fecal transplant through 56 days after completion of study treatment.
Definition of Treatment Failure (CDI Recurrence)	Treatment failure (CDI recurrence) is defined as: 1) the presence of CDI diarrhea, with or without other CDI symptoms, < 56 days after completion of study treatment; 2) a positive stool test for C. difficile ; 3) need for retreatment for C. difficile infection; and 4) no other cause for CDI diarrhea has been determined. [REDACTED]
Determination of Success/Failure	The site investigator makes the determination of success based on: the absence of CDI diarrhea without the need for retreatment with C. difficile anti-infective therapy or FT through 56 days after completion of study treatment. The investigator makes the determination of failure based on 1) the subject's reporting the presence of CDI diarrhea, with or without other CDI symptoms, < 56 days after completion of study treatment; 2) a positive stool test for C. difficile ; 3) need for retreatment for C. difficile infection; and 4) no other cause for CDI diarrhea symptoms is determined.
Medical Monitor Adjudication	The Medical Monitor will adjudicate SAEs and other adverse events of interest to provide an objective, qualified judgment of the events.
Sample Size	[REDACTED] The study will enroll up to approximately 150 subjects to allow for loss-to-follow and additional safety numbers if needed. [REDACTED]
[REDACTED]	[REDACTED]

Blinding	This is an open-label study; no blinding will be employed.
Study Population	The target population is adults ( $\geq 18$ years old) with recurrent CDI who have had either a) at least two recurrences after a primary episode [REDACTED] and have completed at least two rounds [REDACTED] of severe CDI resulting in hospitalization.
Inclusion Criteria for Treatment Subjects	
 
1. <math>\geq 18</math> years old.
 
2. Medical record documentation of recurrent CDI including a positive C. difficile test within 60 days prior to enrollment and either: a) at least two recurrences after a primary episode and has completed at least two rounds of standard-of-care oral antibiotic therapy or b) has had at least two episodes of severe CDI resulting in hospitalization.
 
3. Already taking or will start a course of antibiotics to control recurrent CDI symptoms at the time of enrollment. [REDACTED]
 
4. Willing and able to have an enema(s).
 
5. Willing and able to complete the stool and serum testing required for the study.
 
6. [REDACTED]
 
7. [REDACTED]
 
8. [REDACTED]
 
9. [REDACTED]
 
10. [REDACTED]
 
11. Willing to complete the required Subject Diary.
 
12. Willing and able to meet all study requirements, including completing the assessment visit and phone calls.
 

Exclusion Criteria for Treatment Subjects	
 
1. A known history of continued CDI diarrhea despite being on a course of antibiotics prescribed for CDI treatment.
 
2. Requires continuous antibiotic therapy for a condition other than CDI.
 
3. Previous successful (resolution of CDI diarrhea) fecal transplant for recurrent CDI <math>< 6</math> months prior to study enrollment.
 
4. Previous unsuccessful (recurrent CDI diarrhea was unresolved) fecal transplant.
 

Rebiotix Inc

[REDACTED]

RBX2660 (microbiota suspension)

Protocol 2015-01

v5 20 Jan 16

	[name] www.rebiotix.com [REDACTED]
[REDACTED] [REDACTED] [REDACTED]	[REDACTED] [REDACTED] [REDACTED] [REDACTED] [REDACTED]

CONFIDENTIAL

## 1.0 Introduction

### 1.1 Background

RBX2660 (microbiota suspension) is an intestinal microbial suspension prepared from human stool obtained from carefully and thoroughly screened healthy human donors. It is being studied for the treatment of recurrent *Clostridium difficile* infection (CDI). RBX2660 is prepared from a standardized amount of stool mixed with saline ██████████ ██████████ ██████████

Rebiotix conducted its first clinical study of RBX2660 in an open-label, non-controlled Phase 2 study demonstrating the safety of the product and is currently conducting a prospective, multicenter, randomized, double-blinded, placebo-controlled, 3-arm Phase 2B study designed to demonstrate the efficacy and safety of RBX2660 for the treatment of recurrent CDI. The purpose of this current study is to gather additional efficacy and safety data on the use of RBX2660 for recurrent CDI in subjects who have had either a) at least two recurrences after a primary episode ██████████ and have completed at least two rounds of standard-of-care oral antibiotic therapy or b) have had at least two episodes of severe CDI resulting in hospitalization.

This study will be conducted in compliance with this protocol and each site's governing Institutional Review Board/Research Ethics Board; in accordance to relevant regulations in 21 CFR Part 11, 50, 54, 56 and 312; and the ICH E6 Good Clinical Practice: Consolidated Guidance.

### 1.2 Investigational Agent

██  
██  
██  
██  
One study treatment consists of two doses of RBX2660 administered  $7 \pm 2$  days apart.

### 1.4 Preclinical Data

██  
██  
██  
██  
██

[REDACTED]

**1.6 Treatment Rationale and Risk/Benefit**

This study is assessing RBX2660 as an adjunct to antibiotics for the treatment of recurrent CDI. RBX2660 (microbiota suspension) was developed after careful, controlled component and process testing performed by Rebiotix. [REDACTED]

[REDACTED]

**2.0 Study Objectives and Endpoints**

**2.1 Primary Objective**

To compare the efficacy of one treatment with RBX2660 versus antibiotic-treated historical controls. (One treatment consists of 2 enemas of RBX2660 7 ± 2 days apart.)

**2.2 Secondary Objectives**

1. To evaluate the safety of RBX2660.
2. To evaluate the effect of RBX2660 on pre-existing conditions other than recurrent CDI.
3. To evaluate quality of life as measured by the SF-36 Health Survey.

4. To evaluate the efficacy of *C. difficile* anti-infection therapies administered to confirmed treatment failures.

### 2.3 Primary Endpoint

Efficacy, measured by the recurrence-free rate of CDI diarrhea without the need for retreatment with *C. difficile* anti-infective therapy or fecal transplant through 56 days after completion of study treatment with RBX2660, will be evaluated by comparing the recurrence-free rate observed in the study population to the recurrence-free rate identified from antibiotic-treated historical controls.

### 2.4 Secondary Endpoints

1. The frequencies and severity grades of solicited AEs from the first day of assigned study treatment through seven days following the last enema of assigned study treatment will be collected.
2. Adverse events, including serious adverse events and the onset of new chronic diseases, will be collected at in-office visits at 1, 4 and 8 weeks and at 3-, 6-, and 12-month calls; they will be categorized by frequency, severity, seriousness, and causality.
3. Serious adverse events and new onset of chronic diseases will be collected at a telephone call at 24 months and will be categorized by frequency, severity, seriousness, and causality.
4. Frequencies of major complications of CDI including death, septic shock, toxic megacolon, colonic perforation, emergency colectomy, or ICU admission will be collected through the 24-month telephone assessment.
5. The effect of RBX2660 on pre-existing conditions other than recurrent CDI will be assessed by comparing the change in the condition throughout the course of the study.
6. SF-36 scores recorded at the Week 8 visit will be compared to scores recorded at the screening visit.
7. Efficacy of *C. difficile* anti-infection therapies administered to confirmed treatment failures will be compared to each other for the rates of success at resolving CDI diarrhea for at least 56 days after completion of the anti-infection therapy.

### 3.0 Study Design

#### 3.1 Study Purpose

The purpose of this study is to evaluate the efficacy and safety of RBX2660 for the treatment of recurrent CDI in subjects who have had either a) at least two recurrences after a primary episode (i.e., at least three episodes) and have completed at least two rounds of standard-of-care oral antibiotic therapy or b) have had at least two episodes of severe CDI resulting in hospitalization.

#### 3.2 Study Design

This is a prospective, multicenter, open-label study assessing RBX2660 as an adjunct to antibiotics for the treatment of recurrent CDI. Up to approximately 150 subjects will be enrolled in this study. Efficacy of RBX2660, measured by the recurrence-free rate of CDI diarrhea without the need for retreatment with *C. difficile* anti-infective therapy or fecal transplant through 56 days after completion of study treatment with RBX2660, will be evaluated by comparing the recurrence-free rate observed in the study population to the recurrence-free rate identified from antibiotic-treated historical controls. Subjects who meet all inclusion and exclusion criteria, including having a positive *C. difficile* test within 60 days prior to enrollment and experiencing either a) at least two recurrences after a primary episode and have completed at least two rounds of standard-of-care oral antibiotic therapy or b) have had at least two episodes of severe CDI resulting in hospitalization prior to enrollment, will receive treatment with RBX2660. One study treatment consists of two RBX2660 enemas administered  $7 \pm 2$  days apart (no antibiotics between doses); the second enema may be administered sooner if CDI diarrhea reoccurs in less than 7 days. Subjects will already be taking or will start a course of antibiotics to control recurrent CDI diarrhea at the time of enrollment, [REDACTED]

[REDACTED] An in-office follow-up visit will occur at 8 weeks after completing study treatment for the assessment of AEs, efficacy, collection of the Subject Diary, and blood tests. Telephone assessments for adverse events including SAEs and the new onset of chronic diseases and CDI symptoms will occur at weeks 1, 2, 3, and 4 and at 3, 6, and 12 months after completing study treatment. Assessment of serious adverse events and the new onset of chronic diseases will occur via phone call at 24 months after completing study treatment. Subjects will

keep a detailed Subject Diary to allow for assessment of solicited adverse events (see Section 7.1.3) from the date of enrollment to 1 week after completing study treatment. Treatment failures (as determined by the site investigator at the time of CDI recurrence) are eligible to receive another therapy deemed most appropriate by their study investigator; see “Management of Treatment Failures,” below.

[REDACTED]

**3.4 Definition of CDI Diarrhea**

*Clostridium difficile* diarrhea is defined as the passage of  $\geq 3$  watery stools in  $\leq 24$  hours for at least two consecutive days.

**3.5 Definition of Treatment Success**

Treatment success is defined as: the absence of CDI diarrhea without the need for retreatment with *C. difficile* anti-infective therapy or FT through 56 days after completion of study treatment.

**3.6 Definition of Treatment Failure**

Treatment failure (CDI recurrence) is defined as: 1) the presence of CDI diarrhea (see Section 3.4), with or without other CDI symptoms,  $< 56$  days after completion of study treatment; 2) a positive stool test for *C. difficile*; 3) need for retreatment for *C. difficile* infection; and 4) no other cause for CDI symptoms has been determined. [REDACTED]

[REDACTED]

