### 3.8 Determination of Treatment Success/Failure

The site investigator makes the determination of success based on: the absence of CDI diarrhea without the need for retreatment with *C. difficile* anti-infective therapy or FT < 56 days after completion of study treatment. S/he makes the determination of failure based on the four criteria for treatment failure listed in Section 3.6, above.

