### 3.9 Blinding

This is an open-label study; no blinding will be employed.

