**6.8 8-Week Office Visit (Visit 4)**

Subjects return to the study site for the 8-week follow-up visit after completing study treatment with RBX2660. [REDACTED]

[REDACTED] At this visit, reoccurrence of CDI and adverse event information is assessed, a review of medication changes and pre-existing conditions is conducted, and the SF-36 Form is administered. The assessment of pre-existing conditions includes discussion with the subject to determine if the condition is improved, unchanged, worsened or resolved since completion of study treatment. The Subject Diary is collected and reviewed with the subject. [REDACTED] If CDI reoccurrence is suspected < 56 days after completing study treatment, the investigator assesses for recurrence using the four criteria in Section 3.6. The need for retreatment for *C. difficile* infection in the absence of a positive stool test for *C. difficile* will be made by the study investigator so that the appropriate treatment of the subject can be quickly administered in the case of failure to avoid serious adverse events, including hospitalization or death. If the subject does not have reoccurrence of CDI before 56 days after completing study treatment, s/he is considered a treatment success (see Section 3.5). [REDACTED]

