#### 7.1.2 Anticipated Adverse Events

The following is list of anticipated adverse events that may or may not be causally related to RBX2660, the enema procedure, or CDI:

- gas (flatulence)
- belching
- abdominal distension or bloating
- increased diarrhea
- abdominal cramping or pain
- constipation
- colitis
- fever  $\geq 38.0^{\circ}\text{C}$  ( $100.4^{\circ}\text{F}$ )
- fatigue
- chills
- transmission of disease from the donor to recipient
- rectal irritation or pain
- rectal bleeding
- nausea
- vomiting
- hypotension
- puncture of the intestine

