## 7.2 Assessment of Efficacy

The primary efficacy parameter is treatment success, defined as the absence of CDI diarrhea without the need for retreatment with *C. difficile* anti-infective

therapy or FT through 56 days after the completion of study treatment (Visit 3). Some subjects may continue to have short bouts of diarrhea before the 56-day time point, but most if not all will be resolved within 30 days after receiving RBX2660. The efficacy assessment will occur at the 8-week office visit.

[REDACTED]  
[REDACTED]  
[REDACTED]

[REDACTED] See Sections 6.10 and 8.0 of this protocol and the separate Statistical Analysis Plan for additional details on the efficacy assessment.

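### The success and failure rules do not cover test-positive diarrhea put down to RBX2660 or the enema, and section 6.8 can count it as a success

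*Protocol*

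**What the plan says.** Protocol 3.4 defines CDI diarrhea by stool count alone: three or more watery stools in 24 or fewer "hours for at least two consecutive days". It contains no test and no cause.

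Protocol 3.5 (SAP 4.1.3) builds success on that definition: "Treatment success is defined as: the absence of CDI diarrhea without the need for retreatment", through day 56. It has no cause clause either.

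Protocol 3.6 (SAP 4.1.4) requires four things together for failure: CDI diarrhea before day 56, a positive stool test, a need for retreatment, and "4) no other cause for CDI symptoms has been determined".

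Protocol 3.8 gives both decisions to the site investigator. On failure it says "S/he makes the determination of failure based on the four criteria for treatment failure listed in Section 3.6, above". Section 3.9 adds "This is an open-label study; no blinding will be employed".

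Protocol 6.8 applies the four criteria at week 8 and continues: "If the subject does not have reoccurrence of CDI before 56 days after completing study treatment, s/he is considered a treatment success". That sentence closes with a cross-reference to 3.5.

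Two other passages bear on cause. Section 7.1.2 places increased diarrhea in a list of "anticipated adverse events that may or may not be causally related to RBX2660, the enema procedure, or CDI". Section 7.2, on efficacy, says "Some subjects may continue to have short bouts of diarrhea before the 56-day time point" and expects most or all of these to settle within 30 days after RBX2660.

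**The concern.** The comparison is with chart-review controls and has neither randomization nor blinding, so an outcome rule that leaves little to opinion is one of the few protections it has. Here two of the four failure criteria are opinions of someone who knows the subject received RBX2660, and the protocol supplies that person with a possible explanation for early diarrhea that no control can have.

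The same investigator also judges adverse event causality (7.1.7), and 7.1.5 keeps a recurrence off the adverse event form unless it leads to hospitalization. One unblinded judgment can therefore send an episode either to the adverse event tables or to the primary endpoint. If it goes to the former and 6.8 is read literally, the subject counts towards the recurrence-free rate despite qualifying diarrhea and a positive test.

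**Working it through.** **Step 1: one case under each rule.** Take an RBX2660 subject with diarrhea meeting 3.4 and a positive C. difficile test before day 56. The investigator attributes it to the enema, sees no need for C. difficile retreatment, and gives none.

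| Rule | What it asks | Result |
|---|---|---|
| Protocol 3.5, SAP 4.1.3 | No diarrhea meeting 3.4 and no retreatment | Not a success |
| Protocol 3.6, SAP 4.1.4 | All four criteria | Criteria 3 and 4 unmet: not a failure |
| Protocol 3.8 | Success on the 3.5 test, failure on the four criteria | Neither |
| Protocol 6.8 | Recurrence on the four criteria; without it, success | Success by the sentence, not by its pointer to 3.5 |

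The definitions are not complementary, and 6.8 closes the gap in favor of success unless the pointer is taken to override it.

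**Step 2: is the attribution open to the investigator?** Section 7.1.2 allows it as a possibility. No visible text in 3.6, 3.8, 6.8 or SAP 4.1.4 excludes RBX2660 or the enema as the other cause. The visible remit of the Medical Monitor (7.1.8) covers SAEs and adverse events of interest, not efficacy outcomes.

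**Step 3: does the SAP test it?** Visible SAP 8.7.1 analyzes success in the Evaluable Population, repeats the analysis in the Full Analysis Set and Per Protocol populations, and imputes missing responses as successes. None of these varies the attribution.

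**Step 4: size per subject.** The plan states no figure to reproduce. With up to about 150 RBX2660 subjects (Protocol 8.1), each one scored this way moves the rate by 1/150 = 0.67 points. At the look planned when about 100 have completed week 8 (Protocol 8.3), it is 1/100 = 1.0 point.

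**Step 5: illustration.** Alpha and the assumed rates are not visible, so the following are assumptions: two-sided alpha 0.05, pooled z test, 150 RBX2660 subjects, and 100 or 200 controls (Appendix A7). The control recurrence-free rate is p = 35%, from the 65% recurrence figure in Appendix A3. The true rate is set equal in both groups. A share q of true RBX2660 failures is scored as recurrence-free, so the observed RBX2660 rate is p + (1 − p)q. For q = 10% this is 0.35 + 0.65 × 0.10 = 41.5%.

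| q | Observed RBX2660 rate | Chance of a false win, 100 controls | 200 controls |
|---|---|---|---|
| 0 | 35.0% | 2.5% | 2.5% |
| 10% | 41.5% | 17% | 24% |
| 20% | 48.0% | 53% | 69% |
| 30% | 54.5% | 86% | 96% |

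Simulation with 400,000 runs per case agreed within 1 point. Starting from equal observed rates, reaching p < 0.05 takes 20 of 98 RBX2660 failures rescored against 100 controls, or 17 of 98 against 200. Over control rates of 25% to 55% it takes 14 to 20 subjects (12.5% to 28% of RBX2660 failures). If the true RBX2660 rate is 60% to 80%, q of 10% to 30% inflates it by (1 − rate) × q, that is 2 to 12 points. The documents give no value for q.

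**The case against.** The strongest reply is that 3.5 already settles the case. Qualifying diarrhea defeats success whatever its cause, SAP 8.7.1 makes treatment success the primary efficacy endpoint, and the sentence in 6.8 points back to 3.5. On that reading the subject is not a success and the rate is not inflated. This stands as one possible reading, but the endpoint is also described as a recurrence-free rate, recurrence is defined by 3.6, and 6.8 scores its absence as success. The text supports both readings, which is the defect.

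Second, the exposure is narrow. Another cause must have been determined, so criterion 4 defaults to failure. A subject retreated for C. difficile cannot be a success under 3.5. Section 6.8 stresses prompt treatment, and 7.1.7 tells the investigator to weigh continuing CDI symptoms against a product effect. This limits the problem to untreated episodes that settle, which is close to what 7.2 foresees, although 7.2 neither attributes those bouts to RBX2660 nor says that they meet 3.4.

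Third, a large true effect would absorb the bias. Assuming 70% against 35% with 150 and 100 subjects, the standard error is √(0.7 × 0.3/150 + 0.35 × 0.65/100) = 6.06 points, so the difference is 35/6.06 = 5.8 standard errors. Shifting it by one takes 6.06/0.667, or about nine subjects. That holds for the test under those rates. The reported rate would still be too high.

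Fourth, text is redacted after 3.6 and SAP 4.1.4 and within SAP 4.1.6, 7.2 and SAP 8.7.1, and the body of SAP 7.4 is not visible. An attribution or adjudication rule may sit there. The point is therefore limited to the visible text.

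**Conclusion.** The point holds in limited form. Sections 3.5, 3.6 and 6.8 give three different answers for one foreseeable case, and an attribution available only in the RBX2660 group can raise that group's recurrence-free rate. The size is 0.67 points per subject at n = 150. The number of subjects is unknown, and the false-win figures depend wholly on the assumed q, alpha and control rate.

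A reader might infer three stronger things that the documents do not support:

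- **That the protocol calls RBX2660 and the enema expected causes of diarrhea.** Section 7.1.2 says only that the listed events may or may not be related to them, and it names CDI beside them.
- **That the same episode is scored as a recurrence in a control, so that differential misclassification is shown.** Appendix A4 defines which charts to identify. No control outcome rule is visible, and control charts can record other causes too. Charts may also miss recurrences treated elsewhere, which would raise the control rate, so the net direction of bias in the comparison is not established.
- **That a non-failure is automatically a success.** Under 3.5 it is not. That result comes only from 6.8 read without its cross-reference.

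**What to change.** For endpoint scoring only, leaving care unchanged:

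1. Reconcile Protocol 3.5, 3.6 and 6.8 with SAP 4.1.3, 4.1.4 and 4.1.6 into one rule under which every evaluable subject is either a success or a failure. State that another cause must be documented, and that an effect of RBX2660 or the enema does not count as one. Use one time limit, since 3.5 runs through day 56 and 3.6 stops before it.
2. Add to SAP 8.7.1 a sensitivity analysis that scores as failure every RBX2660 subject with diarrhea meeting 3.4 and a positive stool test through day 56, regardless of criteria 3 and 4. Keep charted control recurrences as failures, and show controls restricted to tested episodes as a second version. A test requirement imposed equally on both groups would not work as the only version: Appendix A4 and A6.1 ask for just one positive test on record, so untested control recurrences would drop out.
3. List every test-positive RBX2660 subject scored as a non-failure, with the cause recorded.

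The cost is a short text change, one table and one listing. Protocol 3.7 already has CDI episodes captured in detail. The downside is that the RBX2660 rate in the sensitivity analysis may be slightly lower, because some carriers whose diarrhea has another origin will count as failures.
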